6 RESEARCH QUESTIONS AND OBJECTIVES

Primary Objective

To assess if the odds of AoRRP are lower among females fully vaccinated with Gardasil before the age of 17 years versus those unvaccinated. *

* In case-control studies, the odds (likelihood) of exposure are typically assessed among cases of a disease and compared with controls. However, given that the odds ratio is the same regardless of how it is defined in terms of marginal probabilities (i.e., probability of exposure given disease or probability of disease given exposure are statistically equivalent), we have chosen to express it as the latter (probability of disease given exposure) to provide a measure of the protective effect of vaccination against RRP. Additionally, given the rare outcome of RRP and the use of incidence density sampling, odds ratio estimates will be interpreted as the corresponding relative risks.

Secondary Objectives:

- 1) To assess annual age-standardized incidence rates of AoRRP (ages 15-29 years) among males and females in Sweden, Denmark, and Norway.
- 2) To assess annual age-standardized incidence rates of JoRRP (ages 0-14 years) among males and females in Sweden, Denmark, and Norway.

Exploratory Objectives:

1) To assess factors associated with risk of AoRRP, including history of external genital warts and socioeconomic factors.

PRODUCT: V501/V503	PROTOCOL/AMENDMENT VERSION NO.: V503-088-01-v1
REVOPS ID NO: NIS009722	CORE DRC APPROVAL DATE: 18JUL2024
EPIDEMIOLOGY NO.(PE STUDIES ONLY): EP08039.017	

7 RESEARCH METHODS

7.1 Study Design

Primary Objective: Nested Case-Control Study

Setting: Sweden, Denmark, Norway.

In all Nordic countries, registries have been established to capture disease and vaccination history, as well as other demographic data. Importantly, all registry data can be linked by a unique PIN that is assigned to each resident at birth (or at the time of immigration) and does not change through the resident's lifetime. Therefore, existing infrastructure and registry systems are an excellent resource for monitoring the burden of HPV-related disease in the general population. Registries are accurate, complete, and have high population coverage, thereby minimizing some biases inherent in observational studies, such as selection of the study population, recall bias, and lack of access to complete medical records.

Design: Population-based nested case-control study. A nested case-control design allows the selection of controls from the same underlying population at risk as the cases, therefore reducing confounding and selection bias. This design is used for studies of rare diseases and is particularly advantageous for studies of biologic precursors of disease [29].

Cohort: AoRRP cases are most often diagnosed between ages 20-40 years [3] and causal HPV infections are likely acquired through sexual behavior like other HPV related diseases [5]. Several age-based cut points have been proposed to distinguish JoRRP from AoRRP (ranging from 11 to 17 years). In this proposed study, we used a cut point of 15 years for AoRRP based on expert opinions that RRP diagnosed before the age of 15 years are likely due to HPV infections acquired during birth from mothers and HPV infections at 15 years and older ages are likely acquired through sexual transmission. The median age at first intercourse among Scandinavian women was 16 years in Denmark and 17 years in Norway and Sweden [28]. An upper age of below 30 (i.e., study including 15-29-year-olds) was chosen by the study team since Gardasil is most efficacious when administered at younger ages.

Gardasil was not available in Sweden, Denmark, and Norway until 2006. Therefore, we plan to capture the cohort of girls/women aged 15 to 29 years beginning 2006 till the most recent registry data are available from each country, which currently is 2021 for Sweden and 2022 for Denmark and Norway. A description and rationale for the age groups, birth cohorts, and calendar years of coverage included for the three participating countries is provided in Table 1 and Figure 1 below.

PRODUCT: V501/V503	PROTOCOL/AMENDMENT VERSION NO.: V503-088-01-v1
REVOPS ID NO: NIS009722	CORE DRC APPROVAL DATE: 18JUL2024
EPIDEMIOLOGY NO.(PE STUDIES ONLY): EP08039.017	

[figure not shown]
Table 1 Description of age groups, birth cohorts, and calendar years of the participants included in the primary and secondary analysis.

Country	Age at diagnosis	Birth cohort	Calendar year – study period
]	Primary analysis (Exposure: HPV vaccination at < 17 years of age)		
Sweden	15 – 29 years	1990 – 2006	2006 through 2021
Denmark	15-29 years	1990 - 2007	2006 through 2022
Norway	15 – 29 years	1990 - 2007	2006 through 2022
Secondary analysis (All available data)			
Sweden	0-29 years	1971 – 2021	2000 through 2021
Denmark	0-29 years	1968 - 2022	1997 through 2022
Norway	0-29 years	1979 - 2022	2008 through 2022

In Figure 1 below, age of participants is represented on the y-axis (horizontal grid lines), calendar year is represented on the x-axis (vertical grid lines), and the birth cohort is represented by the diagonal grid lines and years of birth labelled in the cells. The shaded green areas represent the ages, birth cohorts, and calendar years for the participants included in the study for the primary analysis. Light green shade represents Sweden (with participants followed from the beginning of 2006 through to the end of 2021). Dark green shade represents additional years of coverage for ascertainment of AoRRP outcomes, from the beginning of 2006 through to the end of 2022. Grey shaded areas represent birth cohorts from eligible ages and calendar years of coverage that will not be included in the study as they represent participants who may have received HPV vaccine after 17 years of age. Eligible participants from earlier birth cohorts enter and exit the study period early. For example, a 16-year-old girl born in 1990 will enter the study in 2006 and exit the study in 2019 after reaching the age of 29 years.

PRODUCT: V501/V503	PROTOCOL/AMENDMENT VERSION NO.: V503-088-01-v1
REVOPS ID NO: NIS009722	CORE DRC APPROVAL DATE: 18JUL2024
EPIDEMIOLOGY NO (PESTLIDIES ONLY): EP08039 017	

Figure 1 Lexis diagram to visualize the ages, birth cohorts, and calendar years of coverage of included participants from Sweden, Denmark, and Norway.

As described in Section 5 (above), since 2012 in Sweden, females ages 10-12 years have been targeted for vaccination as part of school-based program, with fully subsidized catch-up vaccination up to age 17 years (partially subsidized for females ages 13-17 years since 2007). In Denmark, vaccination of girls 12 years of age started in January 2009, and catch-up vaccination of girls 13-15 years of age started in October 2008. In 2012, another catch-up program (targeting females up to age 27 years) was implemented. HPV vaccination program was initiated in Norway in 2009, in which girls approximately 12 years of age (i.e., attending the seventh grade) were offered Gardasil in a three-dose schedule (until 2017). Males were not included (or only recently included) in national immunization programs during the study period in Sweden, Denmark, and Norway and therefore due to very low coverage it is not feasible to include males in the study.

Cases: Within the specified cohort, AoRRP (females only) cases (first diagnosis) will be identified from national registries using the ICD-10 code D14.1 (benign neoplasm of larynx). The date of first diagnosis is the index date for AoRRP cases. Compared to JoRRP, other benign laryngeal conditions such as laryngeal granulomas and nodules associated with

PRODUCT: V501/V503	PROTOCOL/AMENDMENT VERSION NO.: V503-088-01-v1
REVOPS ID NO: NIS009722	CORE DRC APPROVAL DATE: 18JUL2024
EPIDEMIOLOGY NO.(PE STUDIES ONLY): EP08039.017	

behaviors such as smoking are likely to be more common among adults and may result in misclassification of the AoRRP outcome based on the use of D14.1 code alone. Therefore, we will use the best practices for accurate ascertainment of AoRRP cases from registries in each participating country to minimize biases after consulting experts and clinicians and reviewing the cases. In countries where topography/morphology codes are available/complete in the cancer/pathology registry, AoRRP definition will require D14.1 and/or appropriate topography/morphology codes.

[figure not shown]
In Sweden, local experts have confirmed that ICD-10 diagnosis code D14.1 (especially subcode A representing "larynx papilloma") is used for diagnosis of RRP and should be used to ascertain AoRRP cases. Experts have recommended use of appropriate topography and SNOMED (Systematized Nomenclature of Medicine) codes to ascertain AoRRP cases more accurately in Denmark. When available and complete, appropriate topography and Norpat (Norwegian Pathology Code system) codes should be used in conjunction with D14.1 to identify AoRRP cases in Norway. Using this approach, we expect the accuracy of RRP diagnosis to be high in Sweden, Denmark, and Norway. The larynx is the site of the vast majority of RRP cases [1] [2], which supports focusing on "benign neoplasm of larynx" rather than other additional sites (ensuring both high sensitivity and specificity of diagnosis).

Where available, the subcode D14.1A will be explored in a subgroup/sensitivity analysis, as this may be more specific for RRP according to clinician expert input. Additionally, cases of D14.1 and/or D14.1A that have at least one associated treatment or procedural code, e.g., DQB10 (Endoscopic extirpation), UDQ25 (Microlaryngoscopy with biopsy), or UDQ22 (Microlaryngoscopy), will also be explored in a subgroup/sensitivity analysis, with similar expectation that this will be more specific for RRP.

Controls: For each case of AoRRP, 10 control subjects free of this diagnosis, at the time of the case's diagnosis, will be identified from the respective countries where cases were diagnosed. As the number of controls per case increases beyond 4, improvement in statistical power diminishes [30]. However, given that data for additional controls are readily available in this database study, 10 controls per case will be selected. Cases and controls will be matched on age (+/- 1 year) at diagnosis, calendar year, and the region where case was diagnosed. By design of the study (nested case-control), cases and controls will also be matched according to length of follow-up in the registries. Controls will be selected from the population at risk at the point in time when a case is diagnosed with RRP. All controls who met the matching criteria will be assigned a random number using SAS statistical software (SAS Institute Inc, Cary, NC) procedures. Then, 10 controls for each case will be selected at random from the pool of eligible controls. Controls will be assigned the same index date as the case to which they are matched. Figure 2 provides an example of case/control subject selection nested within population-based cohort (2006-2021) in this study.

PRODUCT: V501/V503	PROTOCOL/AMENDMENT VERSION NO.: V503-088-01-v1
REVOPS ID NO: NIS009722	CORE DRC APPROVAL DATE: 18JUL2024
EPIDEMIOLOGY NO.(PE STUDIES ONLY): EP08039.017	

Figure 2 Example of case/control subject selection nested within population-based cohort (2006-2021) in this study. Subject 1 is classified as a case without exposure to Gardasil prior to the index (diagnosis) date, and subject 2 is an eligible matched control with exposure to Gardasil prior to the index date.

Exposure assessment: The exposure of interest is GARDASIL or GARDASIL 9 vaccination prior to the index date for each case and matched controls. GARDASIL is a quadrivalent vaccine that is effective against HPV types 6/11/16/18, while GARDASIL 9 is a nonavalent vaccine that is effective against HPV types 6/11/16/18/31/33/45/52/58.

Exposure will be defined in 2 ways:

- 1. Exposure in primary objective: Fully vaccinated with Gardasil (yes/no) before the age of 17 years. A female will be classified as exposed if she received 3 doses of Gardasil (administered at recommended intervals of 0, 2, and 6 months) or 2 doses if <15 years of age (administered at recommended interval of 0 and 6-12 months). For a 3-dose schedule, the minimum intervals are 4 weeks between dose 1 and dose 2 and 12 weeks between dose 2 and dose 3. For a 2-dose schedule, the minimum interval is 5 months between doses. A female will be classified as unexposed if she did not receive even a single dose of Gardasil prior to being selected as a case or control in the study.
- 2. Exposure in sensitivity analysis: Gardasil vaccination (yes/no). A female who received at least one dose of Gardasil prior to the index date will be classified as exposed.

PRODUCT: V501/V503	PROTOCOL/AMENDMENT VERSION NO.: V503-088-01-v1
REVOPS ID NO: NIS009722	CORE DRC APPROVAL DATE: 18JUL2024
EPIDEMIOLOGY NO.(PE STUDIES ONLY): EP08039.017	

The vaccine registries in Sweden, Denmark, and Norway accurately capture vaccination [31], greatly reducing the risk of exposure misclassification and providing the foundation for a robust observational study. Prior studies relying on Nordic registries for measurement of Gardasil exposure (in relation to risk of anogenital diseases, including cervical cancer) have been conducted successfully in recent years [21] [32].

Secondary Objectives: Ecological Study

Design: Descriptive/ecologic study using nationwide registry data to assess annual agestandardized incidence rates of JoRRP (0-14 years) and AoRRP (15-29 years) by gender.

Cohort: Male and female residents of Sweden, Denmark, and Norway (ages 0-29 years), during the following periods (Table 1):

- Sweden: 2000 2021 (birth cohort, 1971 2021)
- Denmark: 1997 2022 (birth cohort, 1968 2022)
- Norway: 2008 2022 (birth cohort, 1979 2022)

Cases: RRP cases will be identified from national registries using the case definitions for the participating countries as described above.

Exposure assessment: There is no exposure for ecologic study (secondary objective).

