	• Sweden: 2000 – 2021 (birth cohort, 1971 – 2021)
	• Denmark: 1997 – 2022 (birth cohort, 1968 – 2022)
	• Norway: 2008 – 2022 (birth cohort, 1979 – 2022)
	Exploratory objective:
	Same population as the primary objective.

PRODUCT: V501/V503	PROTOCOL/AMENDMENT VERSION NO.: V503-088-01-v1
REVOPS ID NO: NIS009722	CORE DRC APPROVAL DATE: 18JUL2024
EPIDEMIOLOGY NO.(PE STUDIES ONLY): EP08039.017	

Variables	Exposure definition:
	Full receipt of GARDASIL/GARDASIL 9 vaccination regimen for effectiveness evaluation (2 or 3 doses according to age at vaccination).
	Outcome definitions:
	• First diagnosis of AoRRP (females only) identified from national registries for primary analysis.
	• First diagnosis of JoRRP and AoRRP (males and females) from national registries for incidence rates assessment in secondary analyses.
	Covariates:
	Vaccination age, history of external genital warts (EGW), and sociodemographic variables (education level, income).
Data Sources	Nordic population, patient, and vaccine registries.
Study Size	Sample size
	Primary objective (nested case-control study):
	Cases: <50 AoRRP cases in each country.
	Controls: 10 controls per case will be selected.
	Secondary objectives (ecological study): Descriptive/no power calculation. Entire age eligible population during specified calendar years in Sweden, Denmark, and Norway will be eligible.
Data Analysis	Power calculation for primary objective:
	A total of 60 AoRRP cases from Sweden, Denmark, and Norway will provide the study with approximately 80% power to detect an odds ratio equal to 3.0 with a corresponding lower bound of 95% CI of odds ratio equal to 1.33.
	Primary analysis:
	Conditional logistic regression for estimation of ORs and corresponding 95% CIs. In the main analysis, only vaccination before 17 years of age will be considered as exposure.

PRODUCT: V501/V503	PROTOCOL/AMENDMENT VERSION NO.: V503-088-01-v1
REVOPS ID NO: NIS009722	CORE DRC APPROVAL DATE: 18JUL2024
EPIDEMIOLOGY NO.(PE STUDIES ONLY): EP08039.017	

Milestones	Planned Date
Start of data collection:	26Oct2021 (Actual)
End of data collection:	3Q2024
Final report of study results:	1Q2025

PRODUCT: V501/V503	PROTOCOL/AMENDMENT VERSION NO.: V503-088-01-v1
REVOPS ID NO: NIS009722	CORE DRC APPROVAL DATE: 18JUL2024
EPIDEMIOLOGY NO.(PE STUDIES ONLY): EP08039.017	

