7.6.1 Exposure

A subject will be defined as fully vaccinated and exposed if she has received 2 or 3 doses (depending on age group-specific dose regimen recommendation) of HPV vaccine with GARDASIL or GARDASIL 9 as defined through the ATC code J07BM01 or J07BM03. Among individuals who initiated vaccination prior to 15 years of age, receipt of 2 doses administered at 0 and 6-12 months is considered fully vaccinated, whereas among individuals who initiate vaccination after 15 years of age, 3 doses administered at 0, 2, and 6 months is considered fully vaccinated. Sensitivity analysis will be performed where individuals will be classified as exposed/vaccinated if they received at least one vaccine dose. The study primary objective/analysis will focus on evaluation of vaccine effectiveness among females fully vaccinated before age 17 years. A female will be classified as unexposed if she did not receive even a single dose of Gardasil prior to being selected as a case or control in the study. Sensitivity analyses will be performed evaluating effectiveness irrespective of age at vaccination, and among those vaccinated at older ages (≥17 years).

PRODUCT: V501/V503	PROTOCOL/AMENDMENT VERSION NO.: V503-088-01-v1
REVOPS ID NO: NIS009722	CORE DRC APPROVAL DATE: 18JUL2024
EPIDEMIOLOGY NO.(PE STUDIES ONLY): EP08039.017	

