7.8 Study Size

Power analysis for the primary objective (nested case-control study):

Estimated power to evaluate the primary objective is presented in this section. Our primary hypothesis is that AoRRP risk is lower among females fully vaccinated with Gardasil before age 17 years versus those who are never vaccinated before case/control selection. This could be also stated as AoRRP risk is higher among females unvaccinated for HPV compared to those who are vaccinated at age < 17 years. The statistical criterion for success requires that the odds ratio (OR) for this comparison be \geq 3.0 and lower bound of the 95% confidence interval (CI) for the OR be \geq 1.33. In observational studies, high effect estimates are considered important to demonstrate strong associations and to assess causality. Conventionally, odds ratios of <2 are considered to represent weaker associations by epidemiologists, as it may not be possible to judge whether the association can be entirely accounted for by bias [39]. A threshold of 3.0 is therefore proposed to establish the effectiveness of Gardasil vaccination in preventing RRP. Prior Nordic registry studies reported Gardasil effectiveness against genital warts ranging from 38%-88% (equivalent to ORs of 1.6-8.3) and cervical intraepithelial neoplasia grade 2+ ranging from 22%-82% (equivalent to ORs of 1.3-4.0) with higher effect among females vaccinated at younger age.

Based on prior available information (i.e., publicly available gross statistics on ICD codes for otorhinolaryngological diseases), the Sponsor's power calculations (summarized below) at first suggested that it may be possible to test this hypothesis in Sweden alone. However, at the time when this protocol was initially drafted, the exact number of cases were not known and therefore it was noted that a decision to conduct the analysis would be made once data were received from the registries, i.e., when the exact number of cases occurring in relevant birth cohorts was confirmed.

Estimated number of AoRRP cases:

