Potential confounders such as highest level of family income and highest level of education achieved by the mother and/or subject income/education (tentatively in tertiles relative to the general age-matched population of the respective countries) will be adjusted for when investigating the primary objective, through inclusion in the conditional logistic regression. Given that most young adult females in their late teens/early 20s in Nordic countries have a similar level of education (i.e., almost all complete high school) and income is often limited due to being in school, adjustment for individual-level income and education will be considered and the decision of which variables to include in the model will depend on association of these variables with RRP outcome, and consideration of collinearity. Additionally, confounder assessment based on G-estimation may be undertaken if considered appropriate following discussion between the Sponsor and investigators.

Sensitivity analyses will be conducted in relation to the primary objective to assess the impact of: vaccine exposure definition (fully vaccinated versus ≥1 vaccine dose), age at

PRODUCT: V501/V503	PROTOCOL/AMENDMENT VERSION NO.: V503-088-01-v1
REVOPS ID NO: NIS009722	CORE DRC APPROVAL DATE: 18JUL2024
EPIDEMIOLOGY NO.(PE STUDIES ONLY): EP08039.017	

vaccination (any age and ≥17 years), applying buffer period between vaccination and disease onset of 6 months (from last dose), outcome definition (ICD-10 code D14.1 only versus cases [of D14.1] that have appropriate topography/morphology or SNOMED/Norpat codes, and cases [of D14.1] with at least one associated treatment/procedural code and/or specified with subcode D14.1.A/"larynx papilloma"), restricted to Gardasil use only (as exposure), and personal history of EGW (yes versus no). OR estimates from the regression model will be inspected in terms of point estimates and precision, for comparison with results from the main analysis. Effect size (OR) estimates are expected to vary across most sensitivity analyses. For example, effectiveness may be higher among females that are fully vaccinated, vaccinated at younger age (prior to sexual debut), without history of EGW, and in analyses including a buffer period and more restrictive outcome definition. For transparency, all preplanned analyses are described here.

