- 1. Separate tables will be prepared with outcome defined using: a) subcode D14.1.A, and b) code D14.1 and/or subcode D14.1A with at least one appropriate procedural code, i.e. DQB10 (Endoscopic extirpation), UDQ25 (Microlaryngoscopy with biopsy), and/or UDQ22 (Microlaryngoscopy).
- 2. Separate tables will be prepared considering: a) age at vaccination (≥17 years vs. any age at vaccination) and b) own history of external genital warts (yes/no).
- 3. Separate tables will be prepared with exposure defined as receiving at least one dose of Gardasil vaccine.
- 4. Separate tables will be prepared applying buffer period between vaccination and disease of 6 months (from last dose).
- 5. Separate tables will be prepared focusing on Gardasil use only as exposure.

¹ All study participants who acquired a first diagnosis of AoRRP as defined for each country.

² 10 controls matched on attained age, region of diagnosis and calendar year of case's diagnosis.

³ Adjustment factors considered for inclusion include education level, income level, country of birth, own history of external genital warts (EGW), and maternal history of EGW.

⁴ A female who received 3 doses (or 2 doses administered at 0 and 6-12 months if <15 years of age) of GARDASIL or GARDASIL 9 before age 17 will be classified as exposed and those who did not receive any dose will be considered unexposed.

PRODUCT: V501/V503	PROTOCOL/AMENDMENT VERSION NO.: V503-088-01-v1
REVOPS ID NO: NIS009722	CORE DRC APPROVAL DATE: 18JUL2024
EPIDEMIOLOGY NO.(PE STUDIES ONLY): EP08039.017	

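### The at-least-one-dose sensitivity exposure in Section 7.1 drops the before-17 limit together with the full-course requirement, so a lower OR could reflect late vaccination rather than fewer doses

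*Protocol*

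**What the plan says.** Section 7.1 (Exposure assessment) fixes two exposure definitions. The primary one is "Fully vaccinated with Gardasil (yes/no) before the age of 17 years", and the reference group is tightly drawn: "A female will be classified as unexposed if she did not receive even a single dose of Gardasil" before selection as a case or control. Women with a partial course, and women first vaccinated at 17 or older, are therefore in neither arm of the primary contrast. The sensitivity definition reads: "A female who received at least one dose of Gardasil prior to the index date will be classified as exposed".

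Two other places repeat the sensitivity definition without giving any age or timing. Section 7.6.1 says "Sensitivity analysis will be performed where individuals will be classified as exposed/vaccinated if they received at least one vaccine dose", and note 3 to Table 5 in Annex 2 says "Separate tables will be prepared with exposure defined as receiving at least one dose of Gardasil vaccine". The Abstract attaches the age limit to the primary analysis: "In the main analysis, only vaccination before 17 years of age will be considered as exposure".

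Section 7.11 lists what the sensitivity analyses are to assess. The first item is "vaccine exposure definition (fully vaccinated versus ≥1 vaccine dose". Age at vaccination (any age, and 17 or older) is a separate item. Each resulting OR is to be compared with the main analysis. The section also expects effectiveness to be higher with a full course and higher with younger age at vaccination, naming these as distinct factors.

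**The concern.** A sensitivity analysis meant to show the impact of the dose definition should change the dose definition and nothing else. As Section 7.1 is written, the at-least-one-dose analysis relaxes two conditions at once. The full course becomes one dose, and the age limit of 17 becomes the index date, which can be as late as age 29.

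The protocol itself expects age at vaccination to matter. Section 7.8 describes earlier Nordic results on genital warts and CIN2+ as showing effectiveness "with higher effect among females vaccinated at younger age", and Section 7.11 expects the same here. If the OR falls from the primary value, a reader who takes the label in 7.11 at face value could put the drop down to incomplete courses when it came from women vaccinated late. The analysis would then not answer the question given for it, and it would overlap with the separate any-age analysis.

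**Working it through.** **1. Text side by side**

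| Feature | Primary (7.1) | Dose sensitivity (7.1) | Purpose (7.11) |
|---|---|---|---|
| Doses | full course | at least one | full course versus at least one |
| Timing | before age 17 | before index date | not mentioned; age is its own item |
| First vaccinated at 17 or older | in neither arm | exposed | – |
| Comparator | – | – | main analysis |

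Two rows change where the stated purpose needs one.

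**2. Can late vaccination occur in the included cohorts?** Yes. Table 1 includes Danish women born from 1990. Those born 1990 to 1992 turned 16 to 18 in 2008 (2008 − 1992 = 16; 2008 − 1990 = 18), when the Danish catch-up for ages 13 to 15 began. They turned 20 to 22 in 2012 (2012 − 1992 = 20; 2012 − 1990 = 22), when the catch-up to age 27 began (Sections 5 and 7.1). The protocol does not say how many were vaccinated then.

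**3. Illustration of size.** The protocol gives no figure for this analysis, so there is none to reproduce. ORs are unvaccinated versus vaccinated and are read as relative risks, as the protocol does; matching and confounding are ignored.

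Inputs:
- OR for vaccination before 17: 3.0 (Section 7.8).
- Full course before 17: 25% (coverage figure in 7.8, taken here as full-course coverage).
- Partial course before 17: 3% (assumed), so f = 0.25 + 0.03 = 0.28.
- No true dose effect: a partial course works as well as a full one (assumed).
- Further share first vaccinated at 17 or older: L = 0.05, 0.10 or 0.20 (assumed).
- OR for late vaccination: 1.3 or 1.6 (assumed; the low ends of the CIN2+ and genital-wart ranges in 7.8).

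Formula: OR(at least one dose, any age) = (f + L) / (f/3.0 + L/OR_late).

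For L = 0.05 and OR_late = 1.3: 0.33 / (0.0933 + 0.0385) = 2.50.

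| L | OR_late 1.3 | OR_late 1.6 |
|---|---|---|
| 0.05 | 2.50 | 2.65 |
| 0.10 | 2.23 | 2.44 |
| 0.20 | 1.94 | 2.20 |

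With the definition limited to doses before 17, the OR is 0.28 / (0.28/3.0) = 3.0, equal to the primary. If late vaccination worked as well as early, the any-age OR would also be 3.0.

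**4. The two explanations can give the same number.** Let w be the share of the exposed group with the weaker effect.
- No dose effect, 20% of the exposed vaccinated late at OR 1.5: 1 / (0.8/3.0 + 0.2/1.5) = 2.50.
- Real dose effect, nobody vaccinated late, 20% of the exposed with a partial course at OR 1.5: the same expression, 2.50.

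The OR alone cannot separate them.

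**5. What the restricted version can deliver.** With 60 cases, 72% unvaccinated, 25% full and 3% partial, all vaccinated at OR 3.0, the case weights are 0.72, 0.25/3 = 0.083 and 0.03/3 = 0.010, total 0.813. Expected cases are 60 × 0.083/0.813 ≈ 6 fully vaccinated and 60 × 0.010/0.813 ≈ 0.7 partly vaccinated. If a partial course did nothing, the partial weight is 0.03 and the total 0.833, giving 60 × 0.03/0.833 ≈ 2 partly vaccinated cases. For the primary contrast with 6 and 54 cases against 150 and 450 controls, OR = (54/6)/(450/150) = 3.0, SE(log OR) = √(1/6 + 1/54 + 1/150 + 1/450) = 0.44, and the unmatched 95% CI is about 1.3 to 7.1. The restricted row will be imprecise and close to the primary.

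**The case against.** The strongest reply is that the any-age reading was probably not intended. Section 7.6.1 lists the at-least-one-dose analysis first and the analyses by age at vaccination separately. Section 7.11 does the same. Note 3 to Table 5 varies a shell whose footnote 4 fixes vaccination before 17, while age is varied in note 2. Read that way, each table changes one factor and only 7.1 lacks a phrase. Much of this stands: 7.6.1 and note 3 are silent on age, so a reader who infers that the protocol sets an any-age definition in three places goes beyond the text. But 7.1 is the only place that states the timing, and it names the index date. A programmer following it would include late vaccination.

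A second reply is that the protocol does not plan to attribute a lower OR to incomplete courses. That also stands. Section 7.11 states an expectation, names age beside dose, and says only that estimates will be inspected for size and precision. A reader might infer that a false dose effect will be reported, but no rule says so.

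A third reply is that the sizes are assumed. They are. Nothing in the protocol shows that late-vaccinated women outnumber those with a partial course before 17. The Danish coverage figures (above 70% in cohorts born from 1985, about 50% under age 17) tempt one to read the gap as late vaccination, but they may refer to different cohorts, and the primary population starts at birth year 1990. The ORs of 1.3 and 1.6 come from other outcomes and are not stated to be late-vaccination effects.

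Finally, the planned any-age and 17-or-older analyses will make an age effect partly visible. The any-age analysis could even serve as a like-for-like comparator if it kept the full course, but the protocol does not say that it does.

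**Conclusion.** The point holds as a mismatch between the definition in 7.1 and the purpose in 7.11. Followed as written, 7.1 changes dose and age together, so a lower OR could reflect late vaccination rather than fewer doses. It does not follow that the analysis will show a false dose effect. That needs an appreciable number of women first vaccinated at 17 or older and weaker protection in them. The protocol expects the second and makes the first possible, but it quantifies neither. Under the stated assumptions, with no dose effect, the OR would be about 2.65 down to 1.9 instead of 3.0. The primary analysis and its success criterion do not depend on this row. The change is worth making because the wording is cheap to correct, but it is not critical to the study's conclusion.

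**What to change.** Define the dose sensitivity analysis as at least one dose of Gardasil before age 17 and before the index date, versus never vaccinated, with women first vaccinated at 17 or older in neither group, as in the primary analysis. State that the any-age and 17-or-older analyses keep the full-course definition, so that each departs from the main analysis in one respect. If the any-age, at-least-one-dose version is still wanted as a broad ever/never check, keep it as an additional row labelled as changing both factors. Align Sections 7.1, 7.6.1 and 7.11 and note 3 to Table 5.

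The cost is about one sentence in each place and one extra table row, using vaccination dates already collected. The restricted row will have slightly fewer exposed women. With so few cases expected after a partial course before 17, it should be presented as a check on the definition and not as an estimate of a dose effect.
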